## Study Protocol and Statistical Analysis Plan

This study is a randomized controlled trial at Magee-Womens Hospital in which individuals with a hypertensive disorder of pregnancy are randomized to the neonatal sleep intervention (the SNOO responsive bassinet), or usual care of safe sleep education in the postpartum period.

*Inclusion and Exclusion Criteria.* Individuals meet inclusion criteria if they are  $\geq 18$  years old, have a singleton, full-term (37 weeks or greater weeks of gestation), live birth of a non-anomalous fetus, a diagnosis of gestational hypertension or preeclampsia by ACOG criteria, are enrolled in the Connected Care (formerly known as Vivify) institutional remote monitoring program, and are willing to undergo randomization and use the SNOO for their neonate. Individuals will be excluded if they are  $< 18$  years old, non-English speaking, having chronic hypertension, pre-gestational diabetes, cardiac disease, kidney disease, or liver disease, have an infant admitted to the NICU, intend to use the SNOO prior to study enrollment, are not willing to be randomized, or are not willing to use the SNOO. Individuals who meet criteria will be approached during their postpartum admission. If the participant agrees to enroll in the study, she will be consented and randomized at that time. Randomization will occur via permuted blocks with randomly varying block sizes by a web-based data entry system.

*Study Overview.* Those randomized to the intervention will be oriented to the use of the SNOO (see Figure 1) and instructed to have their neonate sleep in the SNOO as often as they can, with the understanding that some sleep does occur outside of bassinets. The SNOO is a commercially available device which is a responsive bassinet for neonates, and designed to respond to the infant's cries and automatically respond by emitting engineered white noise sounds and providing a rhythmic rocking motion. The infant is also swaddled to remain securely back-down. The SNOO automatically increases the sound and motion if the infant is still crying. However, if the infant does not settle within 3 minutes, the SNOO shuts off and alerts adults for additional assistance. Parents can also modify the SNOO settings to meet the baby's need for sound and/or motion.

Figure 1: SNOO responsive bassinet

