Participants will be compensated up to \$60 paid on a VINCENT card. They will receive \$50 after completing the 6 week postpartum research visit, and \$10 after completing the 4 month postpartum research study visit.

See a visual representation of the study design in Figure 2:

[figure not shown]

Figure 2: Study Design

**Outcomes.** The primary outcome is mean arterial pressure (MAP) at 6 weeks postpartum. Secondary outcomes include MAP at 1 week and 4 months postpartum; systolic and diastolic BP at 1 week, 6 weeks, and 4 months postpartum; antihypertensive medication use at 1 week, 6 weeks, and 4 months postpartum; Stage 1+ Hypertension or antihypertensive medication use at 1 week, 6 weeks, and 4 months postpartum; maternal weight and body mass index at 1 week, 6 weeks, and 4 months postpartum; subjective sleep quality at 6 weeks postpartum using the PSQI, PROMIS, ESS; objective sleep assessment using sleep log data at 6 weeks and 4 months postpartum; and mood assessment at 6 weeks postpartum using the EPDS, GAD-2, PSS-4, and Breslau-7.

**Sample Size Calculation.** In current remote monitoring patients without a history of chronic hypertension, the mean MAP at 6 weeks (among 1,007 individuals) was  $94 \pm 8$  mmHg. With 1:1 randomization, 2-sided t-test with independent means, a sample size of 100 individuals total (50 per arm) would give an 80% power to detect a 4.5 mm Hg decrease in MAP. Additionally, for our secondary outcomes of systolic and diastolic BP at 6 weeks postpartum, we would be powered to detect a 6 mm Hg decrease in systolic BP and a 5 mm Hg decrease in diastolic BP with an alpha of 0.05, which would be a clinically meaningful outcome.

**Statistical Analysis.** Statistical analysis was performed using the intention-to-treat principle, with all randomized participants included in the analysis. All statistical was performed using Stata (StataCorp LLC, version 17.0, College Station, Texas, USA). Two-sample two-sided t-tests and Mann-Whitney U tests were performed to assess the differences between two groups of continuous, normally-distributed and non-normally distributed variables, respectively. Pearson's chi-square or Fisher's exact tests were performed to assess the differences between two groups of categorical variables. An alpha level of 0.05 was set for all statistical analyses. Pre-specified subgroup analyses include breastfeeding status, postpartum SARS-CoV-2 status, and a per-protocol analysis.

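### Optional improvement, not an error: the primary 6-week MAP comparison is valid but unadjusted; if outcomes are still unanalysed, adjusting for a pre-randomisation MAP could add power at almost no cost

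*Combined protocol and SAP*

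**What the plan says.** The Outcomes paragraph states: "The primary outcome is mean arterial pressure (MAP) at 6 weeks postpartum". The Sample Size Calculation rests on an unadjusted comparison, "With 1:1 randomization, 2-sided t-test with independent means", with 100 participants in total, a 4.5 mm Hg difference and 80% power. The SD comes from the remote-monitoring cohort: "In current remote monitoring patients without a history of chronic hypertension, the mean MAP at 6 weeks (among 1,007 individuals) was" 94 ± 8 mmHg.

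The Statistical Analysis section gives one rule for continuous variables, "Two-sample two-sided t-tests and Mann-Whitney U tests were performed to assess the differences between two groups", and names no covariate or regression model. It opens in the past tense: "Statistical analysis was performed using the intention-to-treat principle, with all randomized participants included in the analysis".

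Under Inclusion and Exclusion Criteria, allocation is described as "Randomization will occur via permuted blocks with randomly varying block sizes by a web-based data entry system", with no stratification factor. The same paragraph says "Individuals who meet criteria will be approached during their postpartum admission" and places consent and randomisation at that point. The Study Overview lists the BP sources: remote-monitoring entries through 6 weeks, and readings at the 6-week and 4-month video visits. It lists no reading taken before randomisation.

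**The concern.** In a trial with a continuous BP outcome, a BP measured before randomisation is the obvious candidate for a prognostic covariate. If it correlates with the 6-week value, adjusting for it removes part of the outcome variance, narrows the confidence interval and raises power without adding a participant or a visit. The plan uses BP in neither the allocation nor the primary model, and it is sized at 80% power with no stated allowance for loss to follow-up. What is at stake is precision. The unadjusted comparison is not biased.

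**Working it through.** **Inputs from the Sample Size and Statistical Analysis sections.** Difference 4.5 mm Hg, SD 8 mm Hg, 50 per arm, two-sided alpha 0.05.

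**Assumed input.** R, the within-arm correlation between pre-randomisation MAP and 6-week MAP. The documents give no value, so a range is shown.

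**Step 1: reproduce the plan.**
- Standard error of the difference: 8 × √(2/50) = 1.60.
- Noncentrality: 4.5/1.60 = 2.8125, on 98 degrees of freedom.
- Power: 79.5% by noncentral t, 80.3% by normal approximation. The stated 80% is confirmed.
- Difference detectable with 80% power: 4.53 mm Hg.
- Expected 95% CI half-width: 1.984 × 1.60 = 3.18 mm Hg.

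**Step 2: add one baseline covariate.** The residual SD becomes 8 × √(1 − R²). One degree of freedom is lost (97 remain). The variance is inflated by 1 + 1/96 = 1.0104 for chance imbalance in the covariate. The standard error is therefore 1.60 × √(1 − R²) × √1.0104. At R = 0.4 this is 1.60 × 0.9165 × 1.0052 = 1.474, the noncentrality is 4.5/1.474 = 3.053, and power is 85.6%.

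| Assumed R | Power | Change from 79.5% (points) | Detectable difference (mm Hg) | CI half-width (mm Hg) |
|---|---|---|---|---|
| 0 | 79.1% | −0.4 | 4.55 | 3.19 |
| 0.2 | 80.7% | +1.2 | 4.46 | 3.13 |
| 0.3 | 82.7% | +3.2 | 4.34 | 3.05 |
| 0.4 | 85.6% | +6.1 | 4.17 | 2.93 |
| 0.5 | 89.2% | +9.7 | 3.94 | 2.76 |

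Adjustment breaks even at R of about 0.10. A simulation with 100,000 trials per cell agrees: 79.1%, 80.8%, 82.7%, 85.7% and 89.1% for the same five values of R.

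**Step 3: allow for missing baselines.** If a fraction m of baselines is missing at random and replaced by the overall mean, the effective correlation is R × √(1 − m). At R = 0.4 power is then 85.0% with 10% missing and 84.3% with 20% missing. At R = 0.3 it is 82.4% and 82.0%. Simulated type I error with 20% imputed was 0.0492, 0.0498 and 0.0507 at R = 0, 0.3 and 0.6, so the imputation does not disturb the test level.

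**The case against.** The strongest reply is that this is a preference. The plan powers a t-test and names a t-test, and no statement in the documents would be contradicted by leaving it so. Any benefit to the primary result also needs three things that are not documented.

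- **Outcomes not yet analysed.** The analysis text says the work was performed. The design text uses the future tense, so this does not prove completion, but it points that way.
- **A usable reading before randomisation.** None is listed as collected. That the admission record holds one is an assumption, resting on the timing of consent during the postpartum stay.
- **A correlation large enough to matter.** It could be weak. The baseline would be an inpatient reading, while later readings are self-recorded. Some participants may also take antihypertensives in between, since the plan lists "antihypertensive medication use at 1 week, 6 weeks, and 4 months postpartum" as a secondary outcome.

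All of this stands. It limits the point to a conditional suggestion but does not remove it, because the worst case costs 0.4 points of power.

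A reader might infer three stronger claims, and the documents support none of them. The first is that the planned test is wrong or the trial underpowered as designed; the test is valid under randomisation and its power reproduces. The second is that the trial ignores baseline blood pressure altogether; eligibility requires gestational hypertension or preeclampsia and excludes chronic hypertension, so baseline hypertensive status enters by restriction. The third is that adjustment will deliver 6 to 10 more points of power; that needs R of 0.4 to 0.5, for which the documents offer no evidence.

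**Conclusion.** The point holds as a low-cost option for the sponsor to consider. BP is neither a stratification factor nor a covariate, and the primary comparison is valid without it. Adjusting for a pre-randomisation MAP would lose at most 0.4 points of power, gain little up to R of about 0.3 (1.2 points at 0.2, 3.2 at 0.3), and gain about 6 to 10 points at R = 0.4 to 0.5. Because the downside is so small, the case does not depend on first establishing R. It does depend on the outcomes being unanalysed and on a suitable reading existing in the admission record. If the outcomes have been analysed, nothing can be gained for the primary result.

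**What to change.** First establish whether outcomes have been analysed.

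**If not, and the admission record holds a BP taken before randomisation:**
- Prespecify the primary analysis as a linear model of 6-week MAP on arm, adjusted for the last MAP before randomisation, and report the adjusted mean difference with its 95% CI.
- Keep the unadjusted t-test as a sensitivity analysis.
- State which reading counts as the baseline. Do not use the 1-week MAP, which is measured after randomisation and may be affected by the intervention.
- Replace a missing baseline by the overall mean without regard to arm, so that nobody is dropped for that reason. This does not deal with missing 6-week outcomes.

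No minimum correlation, linkage to the 1,007-person cohort or term for diagnosis is needed.

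**If outcomes have been analysed:** keep the t-test as primary and report the adjusted model only as a labelled post hoc sensitivity analysis.

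**Cost:** a short SAP addition with the rules for the reading and for missing values, extraction of one BP per participant (100 records), and one degree of freedom. No extra visits or participants are needed.

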Participants receiving the SNOO will be also asked to download and use the SNOO Smart Sleeper mobile application using either their own name and email address (if they are comfortable) or a study-provided ID and email address. This mobile application provides daily sleep reports while the SNOO is in use, alerts the parents that the infant requires additional attention if the infant does not settle after 3 minutes of crying, and allows the parents to customize the sound and/or motion level the infant receives.

Participants both groups will both receive:

- Standard of care safe sleep education during their postpartum admission, including a handout on safe sleeping from the UPMC Healthwise educational database
- Routine postpartum management of their hypertensive disorder of pregnancy, which at Magee-Womens Hospital, consists of enrollment in the Connected Care remote monitoring program.
- BP cuff and a scale with instructions on their use

For both groups, participants will be requested to record vital sign parameters into the Connected Care institutional remote monitoring program through 6 weeks postpartum. There is one main study visit at 6 weeks postpartum, and one brief study visit at 4 months postpartum which will be conducted through video calls. Participants will complete an infant sleep log and a maternal sleep log for the 7 days leading up each of the planned study video visits. At each video visit, participants will be asked to take their weight and blood pressure. At the first video visit, a questionnaire will be administered which includes:

- Pittsburgh Sleep Quality Index (PSQI): 19 questions of subjective sleep quality
- PROMIS Sleep Disturbance Questionnaire: 27 questions regarding sleep quality
- Epworth Sleepiness Scale (ESS): 8 questions to assess daytime sleepiness

- Edinburgh Postnatal Depression Scale (EPDS): 10 questions to identify individuals at risk for postpartum depression
- Generalized Anxiety Disorder 2-Item (GAD-2): 2 questions to screen for generalized anxiety disorder
- Perceived Stress Scale 4 (PSS-4): 4 questions to assess stress level
- Breslau 7-Item (Breslau-7): 7 questions to screen for post-traumatic stress disorder
- Survey questions to assess demographic information, reproductive history, current health status, BP medications, infant feeding method, and SNOO use

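### Antihypertensive use and the hypertension-or-medication composite are tested without stratifying on medication use at randomisation, which forgoes precision that is cheap to recover on secondary outcomes; how much depends on an association the documents do not report

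*Combined protocol and SAP*

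**What the plan says.** The Outcomes paragraph lists two binary secondary outcomes, each at three times, which makes six comparisons: "antihypertensive medication use at 1 week, 6 weeks, and 4 months postpartum", and "Stage 1+ Hypertension or antihypertensive medication use at 1 week, 6 weeks, and 4 months postpartum".

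The Statistical Analysis paragraph gives one rule for such variables, Pearson's chi-square or Fisher's test: "exact tests were performed to assess the differences between two groups of categorical variables". No stratified test, covariate or adjusted model is named for any outcome.

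On timing, the Inclusion and Exclusion Criteria paragraph states: "Individuals who meet criteria will be approached during their postpartum admission". Consent and randomisation follow at that point. On the scheme: "Randomization will occur via permuted blocks with randomly varying block sizes by a web-based data entry system". No stratification factor is given.

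The only collection of medication data described is the questionnaire at the 6-week visit (Study Overview): "Survey questions to assess demographic information, reproductive history, current health status, BP medications, infant feeding method, and SNOO use". No record of medication status at randomisation is described. Women are excluded for "having chronic hypertension, pre-gestational diabetes, cardiac disease, kidney disease, or liver disease". The documents give no rate of antihypertensive use at any time.

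**The concern.** All participants have gestational hypertension or preeclampsia, and some may already be on an antihypertensive when they are randomised. For the medication outcome, status at randomisation is the same variable measured earlier. At 1 week the interval is only days, so later use may largely repeat what was prescribed in hospital. A raw two-group test leaves that predictable variation between women in the error term.

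Precision is scarce with 50 per arm. These outcomes also help a reader judge whether any difference in mean arterial pressure (MAP) was obtained with more or less drug treatment. If medication status at enrolment is not recorded, a difference between arms in later use cannot be set against what was already there at randomisation.

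**Working it through.** **The plan's own figure.** The documents size the trial on MAP only. With SD 8, difference 4.5, two-sided alpha 0.05 and 80% power, n per arm = 2 × (1.96 + 0.8416)² × 8² / 4.5² = 49.6, so 50 per arm. This reproduces the stated 100 in total. No power or precision figure is given for the binary outcomes.

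**Unadjusted precision at 50 per arm.** The half-width of the 95% CI for a risk difference is 1.96 × √(2p(1 − p)/50). At p = 20% it is 15.7 points and at p = 50% it is 19.6 points.

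**What stratifying removes.** Let b be the proportion on medication at randomisation, and let a₁ and a₀ be the proportions with the outcome among baseline users and non-users. With no treatment effect:

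- p = b·a₁ + (1 − b)·a₀
- SE²(raw) = 2p(1 − p)/50
- SE²(stratified) ≈ SE²(raw) − [2b(1 − b)/50] × (a₁ − a₀)²

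The bracket is the variance of the chance imbalance in baseline use between arms. At b = 50% it is 0.01, an SD of 10 percentage points.

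Worked example, 1 week, 90% and 10%: p = 0.50, SE²(raw) = 0.0100, and the removed part is 0.01 × 0.8² = 0.0064. This leaves 0.0036, so the SE goes from 10.0 to 6.0 points.

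All rates below are assumptions, with b = 50%:

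| Setting | a₁, a₀ | SE raw (points) | SE stratified (points) | Reduction |
|---|---|---|---|---|
| Medication, 1 week | 90%, 10% | 10.0 | 6.0 | 40% |
| Medication, 6 weeks | 50%, 5% | 8.9 | 7.7 | 14% |
| Medication, 6 weeks, weak link | 30%, 5% | 7.6 | 7.2 | 6% |
| Medication, later time, weak link | 15%, 3% | 5.7 | 5.6 | 2% |
| Composite driven by blood pressure | 70%, 45% | 9.9 | 9.6 | 3% |

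Simulation at 50 per arm with the Mantel-Haenszel estimator gives slightly smaller reductions: 40%, 13%, 5%, 2% and 3%.

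A composite that follows medication closely would gain more. With b = 40% and composite rates of 100% and 40%, the simulated variance ratio is 0.63, and √0.63 = 0.79, a 21% lower SE.

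**Power, raw chi-square against the stratified test** (simulated, b = 50%, effects assumed):

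| Setting | Raw | Stratified |
|---|---|---|
| 1 week: users 90% to 70%, non-users 10% to 5% | 25% | 45% |
| 6 weeks: users 60% to 30%, non-users 5% | 42% | 50% |
| 6 weeks: users 80% to 50%, non-users 5% | 35% | 53% |
| 6 weeks, weak link: users 30% to 10%, non-users 5% | 34% | 34% |
| Composite, weak link: 70% to 50% and 45% to 25% | 54% | 54% |

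With no effect, both tests reject in about 5% of simulated trials.

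**The case against.** The strongest objection is that the size of the gain rests wholly on assumed rates. That stands. Chronic hypertension is excluded, so treatment may well be stopped within weeks. Low persistence by 6 weeks or 4 months is then at least as admissible an assumption as high persistence, and the gain in that case is a few per cent of the SE. The composite also counts blood pressure, which can dilute the link with baseline medication.

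The largest SE reduction is at 1 week, which is also when a bassinet has had least time to change prescribing. The 25% to 45% power contrast assumes a sizeable effect within days. It illustrates the method and does not forecast this trial.

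Two stronger readings are tempting, and the documents support neither.

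- A reader might infer that all six comparisons are much less precise than they need be. That would require a strong link between baseline medication and outcome throughout. It is plausible at 1 week and uncertain afterwards.
- A reader might infer that chance imbalance at enrolment biases the planned tests, or makes a significant result untrustworthy. It does not. Chance imbalance is already in the unadjusted standard error, and the raw test keeps its error rate near 5%.

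It is also fair to say that a simple, valid test is an acceptable choice for secondary outcomes on which the trial was not sized. What remains is that the stratified analysis costs very little and loses essentially nothing when the link is weak.

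**Conclusion.** The point holds as one of efficiency, limited to two binary secondary outcomes at three times. The planned tests are valid but unadjusted, randomisation is not stratified on medication use, and no record of that status at randomisation is described.

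With half the women assumed on medication at randomisation, stratifying would cut the SE of the risk difference by about 40% at 1 week under strong persistence, about 13% at 6 weeks under moderate persistence, and 2 to 5% where the link is weak. In the weak settings power did not change materially. The documents report neither medication rates nor their association over time, so they cannot say where in this range the trial lies. This is a cheap improvement and does not affect the primary outcome.

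**What to change.** Record antihypertensive use at randomisation (yes/no) from the inpatient medication record for every randomised woman. In the Statistical Analysis section, replace the raw chi-square or Fisher test for antihypertensive use and for the composite, at each time point, with a Mantel-Haenszel risk difference and 95% CI and the Cochran-Mantel-Haenszel test, both stratified by that variable. This keeps the result on the risk-difference scale.

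The section is written in the past tense. If outcomes have already been analysed, keep the planned tests and add the stratified results as a labelled supporting analysis.

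The cost is one chart variable for 100 women and one sentence in the SAP. The only drawback is a short chart look-up.

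### No interaction analysis is specified for the breastfeeding and SARS-CoV-2 subgroups, and per-protocol is listed as a subgroup (low priority)

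*Combined protocol and SAP*

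**What the plan says.** All of this is in the combined protocol and SAP.

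- **Subgroups (Statistical Analysis).** One sentence covers them: "Pre-specified subgroup analyses include breastfeeding status, postpartum SARS-CoV-2 status, and a per-protocol analysis". It attaches no outcome, test or exploratory label.
- **Tests (Statistical Analysis).** For continuous outcomes, t-tests and Mann-Whitney U "tests were performed to assess the differences between two groups of continuous" variables; for categorical outcomes, chi-square or Fisher's exact tests between two groups. The level is common to all: "An alpha level of 0.05 was set for all statistical analyses". No regression model or interaction term appears anywhere.
- **Main analysis population (Statistical Analysis).** "Statistical analysis was performed using the intention-to-treat principle, with all randomized participants included in the analysis".
- **Planned effect (Sample Size Calculation).** With SD 8 mm Hg and 50 per arm, the trial "would give an 80% power to detect a 4.5 mm Hg decrease in MAP".
- **Timing (Inclusion and Exclusion Criteria; Study Overview).** Randomization takes place during the postpartum admission. The only feeding item described belongs to the 6-week questionnaire: "At the first video visit, a questionnaire will be administered which includes" "Survey questions to assess demographic information, reproductive history, current health status, BP medications, infant feeding method, and SNOO use".

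**The concern.** A subgroup analysis asks whether the treatment effect differs between levels of a factor. The methods named can only ask whether the arms differ within a level. One stratum below 0.05 and the other above it does not show that the two effects differ, because each stratum has less power than the whole trial and the two results can easily fall on opposite sides of the threshold. A reader could then conclude that the bassinet works only in breastfeeding mothers, or only in those without infection, when the effect is the same in everyone.

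Two related matters affect interpretation:

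- **Timing of the strata.** If feeding status comes from the 6-week questionnaire, it is recorded after allocation, and a device meant to settle infants might influence it. Postpartum SARS-CoV-2 status may also be fixed after allocation, but no route from a bassinet to infection is evident, so that concern is weaker.
- **Per-protocol.** As usually understood, this is a population selected by adherence, not a level of a participant characteristic. Listing it with the subgroups hides the fact that it is no longer a randomized comparison.

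**Working it through.** **Inputs.** From the Sample Size Calculation: SD 8 mm Hg, 50 per arm, difference 4.5 mm Hg, two-sided test. From Statistical Analysis: alpha 0.05. Assumed, because the documents give no prevalences: splits of 50/50, 70/30, 80/20 and 90/10, equal across arms, so 25/25, 35/15, 40/10 and 45/5 participants per arm in the two strata.

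**Step 1: reproduce the plan's figure.** n per arm = 2(1.96 + 0.8416)² × 8² / 4.5² = 49.6, so 50. Power at 50 per arm is 80.3% by the normal approximation and 79.5% by the noncentral t. The stated 80% is reproduced.

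**Step 2: chance that exactly one stratum is significant when the effect is the same in both.** With p and q the noncentral-t powers in the two strata, this is p(1 − q) + q(1 − p). At 4.5 mm Hg:

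| Split | p | q | Exactly one significant |
|---|---|---|---|
| 50/50 | 0.496 | 0.496 | 0.500 |
| 70/30 | 0.641 | 0.319 | 0.551 |
| 80/20 | 0.700 | 0.222 | 0.611 |
| 90/10 | 0.751 | 0.123 | 0.689 |

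The same calculation at other uniform effects:

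| Effect (mm Hg) | 50/50 | 70/30 | 80/20 | 90/10 |
|---|---|---|---|---|
| 0 | 0.095 | 0.095 | 0.095 | 0.095 |
| 2 | 0.240 | 0.243 | 0.247 | 0.253 |
| 3 | 0.380 | 0.394 | 0.411 | 0.434 |
| 8 | 0.124 | 0.255 | 0.439 | 0.712 |

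The zero row is 2 × 0.05 × 0.95 = 0.095. At 2 and 3 mm Hg the split matters little; at 4.5 and 8 it matters a good deal.

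**Step 3: what an interaction estimate would deliver.** With a and b the stratum sizes per arm, SE = 8 × √(2/a + 2/b). The 95% CI half-width is 1.985 × SE (t on 96 df). Power for a 4.5 mm Hg difference in effect is by the noncentral t.

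| Split | SE | Half-width | Power |
|---|---|---|---|
| 50/50 | 3.20 | 6.35 | 0.285 |
| 70/30 | 3.49 | 6.93 | 0.248 |
| 80/20 | 4.00 | 7.94 | 0.200 |
| 90/10 | 5.33 | 10.59 | 0.133 |

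The interaction test answers the subgroup question at its nominal 5% level for each factor, whatever the common effect. The price is low precision.

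**Step 4: per-protocol.** No arithmetic is needed. The section's governing principle keeps all randomized participants, whereas a per-protocol analysis by its nature drops some according to what they did afterwards. The two do different jobs, and neither is a subgroup of the kind the other two factors define.

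**The case against.** The strongest reply is that the defect is inferred from silence. The section lists general methods and then gives the subgroups one sentence. It never says that arms will be tested within strata, nor that significance in one stratum will be taken as effect modification. That stands: a reader might infer that the plan commits to such claims, and the text does not support it. What remains is that no other method is named, so within-stratum testing is what an analyst following the section would most naturally do.

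Second, the large percentages count how often a pattern appears when the device works equally well in everyone, and harm needs someone to misread it. With no effect the pattern occurs in 9.5% of trials per factor. The upper figures also need a 90/10 split, which puts only 5 participants per arm in the small stratum. All of that stands. It would be wrong to read 50% to 69% as a false-positive rate.

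Third, feeding status might be taken from the delivery admission, and the study design figure, which might show timing, is not visible. So strata formed after randomization are a possibility, not an established fact.

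Fourth, an interaction test has little power at this size. True, but wide intervals show the uncertainty that separate stratum p-values conceal.

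Finally, intention-to-treat already governs, so per-protocol is secondary in practice. That limits the harm but does not make it a subgroup. The plan sets no threshold or data source for adherence, although the app could supply one ("This mobile application provides daily sleep reports while the SNOO is in use"). That is missing detail and does not by itself show the analysis to be wrong.

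**Conclusion.** The point holds as a cheap improvement of low priority. The plan pre-specifies two subgroup factors but names no method that can tell whether the effect differs between their levels, and it classes per-protocol with them.

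If arms are compared within strata, a uniform 4.5 mm Hg effect gives exactly one significant stratum in 50% to 69% of trials, 3 mm Hg in 38% to 43%, and 2 mm Hg in 24% to 25%. These figures rest on the plan's SD and sample size, the assumed splits, and full follow-up of 50 per arm. They describe scope for misreading.

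The documents do not support the stronger conclusions that the plan will claim effect modification, that feeding strata are known to be affected by allocation, or that the trial's main result is compromised. The primary intention-to-treat comparison of 6-week MAP is unaffected.

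**What to change.** In the Statistical Analysis section:

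1. For breastfeeding status and postpartum SARS-CoV-2 status, report the arm-by-subgroup interaction estimate with its 95% CI on 6-week MAP. Label it exploratory, and state that no claim will be made from significance in one stratum.
2. State when each factor was measured. If that was after randomization, as the 6-week questionnaire suggests for feeding, say that the strata may not be protected by randomization.
3. Take per-protocol off the subgroup list and report it as a supportive, non-randomized sensitivity analysis beside the intention-to-treat result.

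The cost is a few sentences and one regression with an interaction term per factor. No new data are needed, so the change remains possible even if enrollment has closed, as the section's past tense may suggest. The downside is that the interaction intervals will be wide (half-width about 6 to 11 mm Hg), power for a 4.5 mm Hg interaction is only 13% to 29%, and stratum p-values can no longer be presented as findings.
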